15.5 Reporting and Exclusions

15.5.1 Evaluation of toxicity: All participants will be evaluable for toxicity from the time of their first treatment.

CONFIDENTIAL

15.5.2 Evaluation of response: All participants included in the study must be assessed for response to treatment, even if there are major protocol treatment deviations or if they are ineligible. Each participant should be assigned one of the following categories: 1) complete response, 2) partial response, 3) stable disease, 4) progressive disease, 5) unevaluable. Patients meeting the eligibility criteria and receiving at least 1 dose of study medication will be included in the main analysis of response rate.

17. APPENDICES

Appendix A: Plasma Preparation SOP

Appendix B: Performance status criteria

Appendix C: Cockcroft-Gault equation

Appendix D: CYP3A4 inhibitors / inducers

[figure not shown]
Appendix E: U.S. Physician Prescribing Information for Erlotinib

Appendix A: Plasma Preparation SOP

NOTE: Time period from draw to freezing of plasma must be less than 3 hours.

[figure not shown]
Baseline plasma preparation (DFCI Longwood)

- 1. Draw 10 mL of venous blood individually into three labelled EDTA tubes, 30 mL total.
- 2. Send one tube of blood to the central laboratory at the Brigham & Women's Hospital Center for Advanced Molecular Diagnostics (CAMD) via Lab Control. Lab Control will then prepare the plasma to be sent to CAMD using their plasma preparation protocol.
- 3. Send the other two tubes of blood to the Clinical Research Laboratory (CRL) at DFCI.
- 4. After receipt of EDTA tubes, the CRL should immediately centrifuge both tubes for 10 minutes at 1500 (+/- 150) x g. NOTE: Break switch must be off so the cell/plasma interface is not disturbed.
- 5. Individually pipette each plasma layer into a 15 mL tube labeled "plasma-1." NOTE: Do not dip the tip of the pipette into the plasma/cell surface and leave a thin plasma layer intact over the interface.
- 6. Centrifuge the two 15 mL tubes containing only plasma for 10 minutes at 3000 (+/-150) x g.
- Use a fresh pipette tip to transfer the supernatant of each of the two tubes into two other 15 mL tubes labeled "plasma-2." NOTE: Leave about 0.3 mL of plasma in each centrifuged 15 mL tube. This leftover 0.3 mL contains cellular debris.
- 8. Label 8 cryovials with study ID, draw date, clinical trial #, and draw ID (Screen-IA, Screen-IB).
- Use a fresh pipette tip to transfer plasma from each "plasma-2" tube into a maximum of four 3.6 mL cryovials per tube of blood (recommend 1 mL plasma per cryovial, total of 8 cryovials).
- 10. Freeze immediately upright at -70C or colder until pick-up by Translational Research Laboratory.

Baseline plasma preparation (other sites)

- 1. Draw 10 mL of venous blood individually into three labelled EDTA tubes, 30 mL total.
- 2. Immediately centrifuge all three tubes for 10 minutes at 1500 (+/- 150) x g. NOTE: Break switch must be off so the cell/plasma interface is not disturbed.
- 3. Individually pipette each plasma layer into a 15 mL tube labeled "plasma-1." NOTE: Do not dip the tip of the pipette into the plasma/cell surface and leave a thin plasma layer intact over the interface.
- 4. Centrifuge the three 15 mL tubes containing only plasma for 10 minutes at 3000 (+/-150) x g.
- 5. Use a fresh pipette tip to transfer the supernatant of each of the three tubes into three other 15 mL tubes labeled "plasma-2." NOTE: Leave about 0.3 mL of plasma in each centrifuged 15 mL tube. This leftover 0.3 mL contains cellular debris.
- 6. Label 2 cryovials with patient MRN, study ID, draw date, and clinical trial #. Label four cryovials with study ID, draw date, clinical trial #, and draw ID (Screen-IA, Screen-IB).
- 7. Use a fresh pipette tip to transfer plasma from each "plasma-2" tube into at least two 3.6 mL cryovials per tube of blood (recommend 2 mL plasma per cryovial, total of 6 cryovials).
- 8. Freeze immediately upright at -70C or colder until shipping.
- 9. Place the two cryovials labeled with patient MRN in a transport container with dry ice and ship via FedEx courier service to CAMD. Include an EPIC requisition form if shipping from a Partners hospital. Also, send an email to [contact] with patient name, MRN, and the time of shipment.
- 10. Send the remaining four cryovials to the Translational Research Laboratory.

Follow-up plasma preparation (DFCI + outside hospital)

- 1. Draw 10 mL of venous blood individually into one labelled EDTA tube.
- 2. For DFCI Longwood samples, send the tube of blood to the Clinical Research Laboratory for the next step. For other sites, skip this step and proceed to the next step.
- 3. Immediately centrifuge the EDTA tube for 10 minutes at 1500 (+/- 150) x g. NOTE: Break switch must be off so the cell/plasma interface is not disturbed.
- 4. Individually pipette the plasma layer into a 15 mL tube labeled "plasma-1." NOTE: Do not dip the tip of the pipette into the plasma/cell surface and leave a thin plasma layer intact over the interface.
- 5. Centrifuge the 15 mL sstube with only plasma for 10 minutes at 3000 (+/- 150) x g.
- Use a fresh pipette tip to transfer the supernatant into a second 15 mL tube labeled "plasma-2." NOTE: Leave about 0.3 mL of plasma in the centrifuged 15 mL tube. This leftover 0.3 mL contains cellular debris.
- 7. Label the cryovials with study ID, draw date, clinical trial #, and draw ID (usually cycle #).
- 8. Use a fresh pipette tip to transfer plasma from the "plasma-2" tube into a maximum of two-four 3.6 mL cryovials per tube of blood (recommend 1-2 mL of plasma per cryovial, total 2-4 cryovials).
- 9. Freeze immediately upright at -70C or colder until shipment to or pick-up by Translational Research Laboratory.

Appendix B: Performance Status Criteria

ECOG Performance Status Scale		Karnofsky Performance Scale		
Grade	Description	Percent	Description	
0	Normal activity. Fully active, able to carry on all pre-disease performance	100	Normal, no complaints, no evidence of disease.	
0	without restriction.	90	Able to carry on normal activity; minor signs or symptoms of disease.	
1	Symptoms, but ambulatory. Restricted in physically strenuous activity, but ambulatory and able to carry out work	80	Normal activity with effort; some signs or symptoms of disease.	
of a light or sedentary nature (e.g., light housework, office work).	70	Cares for self, unable to carry on normal activity or to do active work.		
2	2 In bed < 50% of the time. Ambulatory and capable of all self-care, but unable to carry out any work activities. Up	60	Requires occasional assistance, but is able to care for most of his/her needs.	
	and about more than 50% of waking hours.	50	Requires considerable assistance and frequent medical care.	
3	In bed >50% of the time. Capable of only limited self-care, confined to bed		Disabled, requires special care and assistance.	
or chair more than 50% of waking hours.	30	Severely disabled, hospitalization indicated. Death not imminent.		
4	4 100% bedridden. Completely disabled. Cannot carry on any self-care. Totally confined to bed or chair.		Very sick, hospitalization indicated. Death not imminent.	
			Moribund, fatal processes progressing rapidly.	
5	Dead.	10 0	Dead.	

Appendix C: Cockcroft-Gault equation

CrCl for males (mL/min) =	[140 - age (years)] X [weight (kg) ¹] (72) X [Serum creatinine (mg/dL)]
CrCl for females (mL/min) =	(0.85) X [140 - age (years)] X [weight (kg) ¹] (72) X [Serum creatinine (mg/dL)]
For SI units: CrCl for males (mL/min) =	[140 - age(years)] X [weight(kg) ¹] X (1.23) [serum creatinine (µmol/L)]
CrCl for females (mL/min) =	[140 - age(years)] X [weight(kg)¹] X (1.05) [serum creatinine (µmol/L)]

¹ If the subject is obese (> 30% over ideal body weight), use ideal body weight in calculation of estimate CrCl

Appendix D: CYP3A4 inhibitors / inducers

CYP3A4 inhibitors			
Acetominophen	Diltiazem	Lovastatin	Progesterone
Acetazolamide	Disulfiram	Mefloquine	Propofol
Amioderone	Docetaxel	Mestranol	Propoxyphene
Amlodipine	Doxorubicin	Methadone	Quinidine
Amprenavir	Doxycycline	Methimazole	Quinine
Anastrozole	Drospirenone	Methoxsalen	Quinupristin
Aprepitant	Efavirenz	Methylprednisolone	Rabeprazole
Atazanavir	Enoxacin	Metronidazole	Risperidone
Atorvastatin	Entacapone	Miconazole	Ritonavir
Azelastine	Ergotamine	Midazolam	Saguinavir
Azithromycin	Erythromycin	Mifepristone	Selegiline
Betamethasone	Ethinyl estradiol	Mirtazapine	Sertraline
Bortezomib	Etoposide	Mitoxantrone	Sildenafil
Bromocriptine	Felodipine	Modafinil	Sirolimus
Caffiene	Fentanyl	Nefazodone	Sulconazole
Cerivastatin	Fluconazole	Nelfinavir	Tacrolimus
Chloramphenicol	Fluoxetine	Nevirapine	Tamoxifen
Chlorzoxazone	Fluvastatin	Nicardipine	Telithromycin
Cimetadine	Fluvoxamine	Nifedipine	Teniposide
Ciprofloxacin	Fosamprenavir	Nisoldipine	Testosterone
Cisapride	Glyburide	Nitrendipine	Tetracycline
Clarithromycin	Grapefruit juice	Nizatidine	Ticlopidine
Clemastine	Haloperidol	Norfloxacin	Tranylcypromine
Clofazimine	Hydralazine	Olanzapine	Trazodone
Clotrimazole	Ifosfamide	Omeprazole	Troleandomycin
Clozapine	Imatinib	Orphenadrine	Valproic acid
Cocaine	Indinavir	Oxybutynin	Venlafaxine
Cyclophosphamide	Irbesartan	Paroxetine	Verapimil
Cyclosporine	Isoniazid	Pentamidine	Vinblastine
Danazol	Isradapine	Pergolide	Vincristine
Delavirdine	Itraconazole	Phencyclidine	Vinorelbine
Desipramine	Ketoconazole	Pilocarpine	Zafirlukast
Dexmedetomidine	Lansoprazole	Pimozide	Ziprasidone
Diazepam	Lidocaine	Pravastatin	1
Diclofenac	Lomustine	Prednisolone	
Dihydroergotamine	Losartan	Primaguine	
CYP3A4 inducers			
Aminoglutethimide	Nevirapine	Phenytoin	Rifapentine
Carbamazapine	Oxcarbazepine	Primidone	- map entitie
Fosphenytoin	Pentobarbital	Rifabutin	
St. John's wort	Phenobarbital	Rifampin	

(Adapted from Cytochrome P-450 Enzymes and Drug metabolism. In: Lacy CF, Armstrong LL, Goldman MP, Lance LL eds. Drug Information Handbook 12TH ed. Hudson, OH; LexiComp Inc. 2004: 1619-1631.)

- Eriotinib solubility is pH dependent. Drugs that alter the pH of the upper GI tract may alter the solubility of eriotinib and hence its absorption. (7)
- Cigarette smoking decreases erlotinib plasma concentrations (7)

See 17 for PATIENT COUNSELING INFORMATION.

Revised: [4/2010]

- 8.3 Nursing Mothers
- 8.4 Pediatric Use
- 8.5 Geriatric Use 8.6 Gender
- 8.7 Race
- 8.8 Patients with Hepatic Impairme 8.9 Patients with Renal Impairment
- OVERDOSAGE
- 10 11 DESCRIPTION
- CLINICAL PHARMACOLOGY 12
- 12.1 Mechanism of Action 12.3 Pharmacokinetics
- 13
 - NONCLINICAL TOXICOLOGY
- 13.1 Carcinogenesis, Mutagenesis, Impairment of Fertility CLINICAL STUDIES 14
 - 14.1 Non-Small Cell Lung Cancer (NSCLC) TARCEVA monotherapy administered as maintenance treatment 14.2 NSCLC TARCEVA administered as a Single-agent 14.3 NSCLC TARCEVA Administered Concurrently with

 - Chemotherapy 14.4 Pancreatic Cancer TARCEVA Administered Concurrently with
- Gemcitabine 16 HOW SUPPLIED/STORAGE AND HANDLING
- 17 PATIENT COUNSELING INFORMATION

*Sections or subsections omitted from the full prescribing information are not listed.

DOSING LOG

-		
C	ICLA.	
U	CIC.	

Erlotinib For each dose take: ____

Please indicate the date, time, amount taken and any comments.

1			
	Date	Amount Taken	Comments
Day 1	Dute	Timbunt Tunch	Comments
Day 2			
Day 3			
Day 4			
Day 5			
Day 6			
Day 7			
Day 8			
Day 9			
Day 10			
Day 11			
Day 11 Day 12			
Day 12 Day 13			
Day 13 Day 14			
Day 14 Day 15			
Day 15 Day 16			
Day 17			
Day 17 Day 18			
Day 19 Day 19			
Day 19 Day 20			
Day 20 Day 21			
Day 21 Day 22			
Day 22 Day 23			
Day 23 Day 24			
Day 25			
Day 26			
Day 27			
Day 27 Day 28			
Day 29			
Day 30			
Day 30 Day 31			
Day 32			
Day 32 Day 33			
Day 33 Day 34			
Day 34 Day 35			
Day 35 Day 36			
Day 30 Day 37			
Day 37 Day 38			
Day 39			
Day 39 Day 40			
Day 40 Day 41			
Day 42			

Participant Identifier:		
Protocol # : 16-093		
Your MD	Phone	
Your RN	Phone	

STUDY DRUG INSTRUCTIONS:

Study Drug: Erlotinib How Much: Your dose is How Often: You will take each dose once daily When: You should take your dose around the same time each day SPECIAL INSTRUCTIONS: Take erlotinib at least one hour before or at least two hours after the ingestion of a meal (on an empty stomach). Take erlotinib with at least an eight ounce glass of water. Do not eat grapefruit or drink grapefruit juice while you are being treated with erlotinib. Take erlotinib about the same time of day. Some over-the-counter (OTC) drugs should be avoided while taking erlotinib. Check with your research team before starting any new OTC drug. If you forget to take a dose of erlotinib, take the drug as soon as you remember, as long as it is at least 12 hours before the next dose is due to be taken the following day. Store the erlotinib tablets in the original container at room temperature, away from heat and moisture. Keep erlotinib tablets away from children and pets. If you should vomit after taking erlotinib, you can re-take the dose within 30 minutes of vomiting. If more than 30 minutes has passed, the dose will be skipped. Please contact your study nurse or MD for additional instructions.

Participant Signature:

Date:

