6.2 Agent Administration & Storage

6.2.1 Erlotinib

Erlotinib will be administered orally on a continuous schedule with a dose of 150 mg po daily on a 6 week cycle of treatment. The beginning of any cycle of treatment may be delayed at the clinical provider's discretion for the treatment of therapy-related toxicities. Dose modification at the beginning of any cycle may be performed due to toxicity as described (7. Expected Toxicities and Dosing Delays/Modifications). If participants neglect to take a dose, they will be instructed to take the dose if there is more than 12 hours until the next dose. If a dose is vomited within 30 minutes of taking it, the participant will be instructed to utilize an anti-emetic and repeat the dose. Tablets should not be crushed, split, or dissolved in water.

Erlotinib tablets will be provided by the study at the appropriate dosage in 6 week cycles with overage. The tablets should be stored at room temperature. No pre-medication is required for treatment.

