6.4 General Concomitant Medication and Supportive Care Guidelines

Participants should receive all appropriate supportive care at the discretion of their primary oncologist (e.g. topical steroids, antibiotics, anti-emetics, g-csf, transfusions). Concomitant use of full-dose anticoagulation using low-molecular weight heparin or other indicated anticoagulation is permitted with the exception of warfarin (see below). Treatment of skin toxicities including topical corticosteroids and topical/oral antibiotics is encouraged. The use of oral corticosteroids is discouraged for skin toxicity \leq grade 2 but may be used at the discretion of the oncologist. Use of corticosteroids to treat brain metastases is prohibited at study entry.

In addition, the following concomitant therapies are discouraged from the study due to known interactions:

- Grapefruit juice (CYP3A4 inhibitor which may increase erlotinib levels and increased toxicity)
- Ciprofloxacin (CYP3A4 and CYP1A2 inhibitor which may increase erlotinib levels and increased toxicity)
- Cigarette smoking should be actively discouraged and all appropriate cessation methods employed. Smoking may induce CYP1A2 and result in lowered erlotinib levels and thus decreased effectiveness.
- Other significant CYP3A4 inhibitors or inducers (Appendix D)
- Other anti-neoplastic systemic therapies
- Warfarin

The absorption of erlotinib may also be dependent on gastric pH and thus the use of proton pump inhibitors (PPI) such as omeprazole should be limited as it may decrease the bioavailability of the drug. However, the use of PPIs is not explicitly excluded but if medically necessary should be maximally separated from the erlotinib dose although this may still result in reduced bioavailability. Additional potential drug-drug interactions should be reviewed by the enrolling sub-investigator as per standard of care and medications discontinued as appropriate (please refer to erlotinib FDA package insert for full list of potential drug-drug interactions).

6.5 **Duration of Therapy**

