8. DRUG FORMULATION AND ADMINISTRATION

8.1 Erlotinib

8.1.1 Description

Erlotinib is a small molecule tyrosine kinase inhibitor with activity against EGFR. The half-life of erlotinib is 36.2 hours. Approximately 83% of the erlotinib dose is eliminated in the feces and approximately 8% is excreted in the urine.

Refer to the Product Information Sheet for information regarding the physical and chemical properties of erlotinib hydrochloride, tablets, and list of excipients.

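### The participant dosing log misstates the vomiting rule in section 6.2.1: it counts 30 minutes from vomiting instead of from intake, and leaves out the anti-emetic

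*Combined protocol and SAP*

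**What the plan says.** Section 6.2.1 gives the protocol rule: "If a dose is vomited within 30 minutes of taking it, the participant will be instructed to utilize an anti-emetic and repeat the dose". The 30 minutes run from intake to vomiting. The section puts no limit on the delay between vomiting and the repeat, and it says nothing about a dose vomited later than 30 minutes.

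The dosing log at the end of the protocol, after Appendix E, carries the instructions that the participant signs. After any vomiting following a dose, it says "you can re-take the dose within 30 minutes of vomiting". It continues: "If more than 30 minutes has passed, the dose will be skipped". That second sentence does not say what the 30 minutes are counted from. The log mentions no anti-emetic. It also says "You will take each dose once daily" and closes the vomiting instruction with "Please contact your study nurse or MD for additional instructions". The form has lines for the physician's and nurse's telephone numbers.

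No other part of the document reconciles the two rules.

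**The concern.** Both texts use 30 minutes but attach it to different intervals. The log appears meant to carry section 6.2.1 to the participant, since its missed-dose instruction follows the 12-hour rule in that section closely. The vomiting line keeps the number and moves the starting event.

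The log is what the participant has in hand at home when the question arises. Followed as written, it can lead to a skipped dose where the protocol calls for a repeat, or to a second full dose on the same day where the protocol provides for none. The situation is foreseeable. The label excerpt in Appendix E lists vomiting among the most common reactions (over 20%) in second-line NSCLC, section 3.1.6 admits previously treated patients, and section 6.2.1 supplies tablets with overage.

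**Working it through.** No formula or sample-size figure is involved, so the check applies both rules to the same cases. Let t1 be the minutes from intake to vomiting and t2 the minutes from vomiting to re-dosing.

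- **Section 6.2.1:** repeat, with an anti-emetic, if t1 is at most 30. There is no condition on t2, and no rule is stated for t1 above 30.
- **Dosing log, natural reading:** re-take allowed if t2 is at most 30, otherwise skip. There is no condition on t1 and no anti-emetic. This reading is natural because the sentence before the skip instruction counts from vomiting.

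| Case | t1 | t2 | Section 6.2.1 | Log, natural reading | Result |
|---|---|---|---|---|---|
| 1. Intake 08:00, vomiting 08:10, re-dosing possible 08:45 | 10 | 35 | Repeat, with anti-emetic | Skip (window closed at 08:40) | Explicit contradiction |
| 2. Intake 08:00, vomiting 14:00, re-dosing 14:20 | 360 | 20 | No repeat provided; silent | Re-take allowed | Conflict by implication |
| 3. Early vomiting, prompt re-dosing | 10 | 10 | Repeat, with anti-emetic | Re-take allowed | Agree, except for the anti-emetic |
| 4. Late vomiting, late re-dosing | 120 | 45 | No repeat provided; silent | Skip | No conflict |

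Case 1 rests on stated text on the protocol side and does not depend on any silence there. It can also arise from following section 6.2.1 itself: a participant who takes the anti-emetic and waits for it to work may pass the log's 30 minutes.

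Case 2 is weaker. The log gives a permission, and section 6.2.1 gives no rule. That section provides for a repeat only after early vomiting, so no repeat is the reasonable inference, but it is not stated.

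The skip sentence can be read in other ways:

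- **Counted from intake to re-taking:** case 1 gives 10 + 35 = 45 minutes, so the log again says skip.
- **Counted from intake to vomiting:** 10 minutes does not trigger the skip. The 30-minute permission has lapsed, but the log then gives no instruction.
- **The 30 minutes describing the dose itself**, that is, a dose taken no more than 30 minutes before vomiting: this reproduces the window in section 6.2.1, though the grammar is strained.

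The contradiction in case 1 therefore belongs to the natural reading and to one of the others, not to every possible reading.

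**The case against.** The strongest defence is that the log is a garbled copy of the right rule and that safeguards surround it. Section 6.2.1 has the participant instructed by staff, the log refers the participant to the nurse or physician, and telephone lines are on the form. Section 6.4 leaves supportive care to the oncologist ("Participants should receive all appropriate supportive care at the discretion of their primary oncologist"), so the missing anti-emetic is an omission rather than a conflict.

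Much of this stands. The safeguards lower the risk, and the anti-emetic is indeed an omission. They do not correct the rule. The referral to staff follows a definite instruction, on which a participant may act without calling, and correct oral advice would then disagree with the sheet at home. The once-daily line does not settle whether a vomited dose counts.

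Three stronger conclusions are tempting, and the documents do not support them:

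- **That the two rules are opposite whenever vomiting is late.** Section 6.2.1 is silent there, not prohibitive.
- **That no reading of the log matches the protocol.** The last reading above does.
- **That the excess exposure or harm can be sized.** Section 8.1.1 states "The half-life of erlotinib is 36.2 hours", which invites a calculation. The documents do not say how much of a vomited dose is retained or how fast it is absorbed, and any answer would shift with the time of the re-take. Section 7.2 notes that overdose has no known antidote, but nowhere is a second 150 mg dose on one day called an overdose.

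**Conclusion.** The inconsistency is real and worth correcting. It contains one explicit contradiction, early vomiting with re-dosing more than 30 minutes afterwards, and one implied conflict, a second full dose permitted after late vomiting. Both rest on reading the log's skip sentence as time since vomiting, which is the natural reading but not the only one. The log also omits the anti-emetic.

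The documents give no frequency for either event and no measure of harm, so the size is limited to what the instruction permits: one skipped or one repeated 150 mg dose per episode.

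A reader might infer that the efficacy result is at risk. Nothing in the documents supports that. The response-rate endpoint, the rule of at least 17 responses in 30 patients and the sample size do not depend on this instruction.

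**What to change.** Reword the vomiting line of the dosing log to: *If you vomit within 30 minutes of taking erlotinib, use the anti-emetic your study team has given or approved and repeat the dose; if you vomit later than that, do not repeat the dose and take the next one at the usual time.*

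Add the same late-vomiting sentence to section 6.2.1. Without it, the log would contain a prohibition that the protocol does not, and the two would differ again. Because the protocol is silent on late vomiting, the investigator should confirm that no repeat is the intended rule.

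The words *given or approved* fit section 6.4 and the log's own line "Check with your research team before starting any new OTC drug".

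The cost is one sentence in each place and a routine IRB submission, since section 14.1 requires IRB approval of amendments before use. Design, sample size and analysis do not change.
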